#### 6.13.4. Clinical Laboratory Evaluation

Clinical laboratory assessments include hematology, serum chemistry, urinalysis, and safety-related immune markers.

By-patient listings of all laboratory test values, and abnormal laboratory test results (criteria defined below) for parameters of special interest (hepatic, leukocytes and platelets) will be provided (Analysis population: FAS Population). Both international system of unit (SI) and conventional unit will be listed when the SI and the conventional units are different.

##### 6.13.4.1. Hepatic Tests

Categories in abnormal hepatic laboratory test results (including scheduled visits, unscheduled visits, and repeat measurements) using Performing Lab Reference Ranges are defined as:

- Abnormal alanine aminotransferase (ALT) or aspartate aminotransferase (AST):  $>1 \times$  upper limit of normal (ULN) to  $<3 \times$  ULN,  $\geq 3 \times$  ULN to  $<5 \times$  ULN,  $\geq 5 \times$  ULN to  $<10 \times$  ULN,  $\geq 10 \times$  ULN to  $<20 \times$  ULN, and  $\geq 20 \times$  ULN
- Total bilirubin:  $>1 \times$  ULN to  $<1.5 \times$  ULN,  $\geq 1.5 \times$  ULN to  $<2 \times$  ULN, and  $\geq 2 \times$  ULN.
- Alkaline phosphatase (ALP):  $>1 \times$  ULN to  $<1.5 \times$  ULN, and  $\geq 1.5 \times$  ULN.

In addition, a by-patient listing of patients who meet any of the following criteria will be provided (Analysis population: FAS Population):

- Elevated hepatic criteria: defined as maximum ALT  $\geq 3 \times$  ULN and maximum total bilirubin  $\geq 2 \times$  ULN within the same study period
- An ALT or AST  $\geq 3 \times$  ULN
- A total bilirubin  $\geq 2 \times$  ULN
- An ALP  $\geq 1.5 \times$  ULN

The listing will include the following information: patient demographics, concomitant medications, ALT/AST/total bilirubin/ALP/ GGT by visit, treatment start and stop dates, and reason for treatment discontinuation.

##### 6.13.4.2. Leukocytes (WBC) and Platelets

Categories in abnormal leukocytes (total leukocytes, neutrophils, and lymphocytes) and platelets laboratory test results (including scheduled visits, unscheduled visits, and repeat measurements) are defined as:

- Leukocytes (total leukocytes):  $<$  lower limit of normal (LLN) to  $\geq 3.0 \times 10^9/L$  (Grade 1),  $<3.0 \times 10^9/L$  to  $\geq 2.0 \times 10^9/L$  (Grade 2),  $<2.0 \times 10^9/L$  to  $\geq 1.0 \times 10^9/L$  (Grade 3), and  $<1.0 \times 10^9/L$  (Grade 4).
- Neutrophils (absolute neutrophils):  $<$  LLN to  $\geq 1.5 \times 10^9/L$  (Grade 1),  $<1.5 \times 10^9/L$  to  $\geq 1.0 \times 10^9/L$  (Grade 2),  $<1.0 \times 10^9/L$  to  $\geq 0.5 \times 10^9/L$  (Grade 3), and  $<0.5 \times 10^9/L$  (Grade 4)

4). Absolute neutrophils will be derived by adding segmented neutrophils and band neutrophils.

- Lymphocytes:  $< \text{LLN}$  to  $\geq 0.8 \times 10^9/\text{L}$  (Grade 1),  $< 0.8 \times 10^9/\text{L}$  to  $\geq 0.5 \times 10^9/\text{L}$  (Grade 2),  $< 0.5 \times 10^9/\text{L}$  to  $\geq 0.2 \times 10^9/\text{L}$  (Grade 3), and  $< 0.2 \times 10^9/\text{L}$  (Grade 4)
- Platelets:  $< \text{LLN}$  to  $\geq 75.0 \times 10^9/\text{L}$  (Grade 1),  $< 75.0 \times 10^9/\text{L}$  to  $\geq 50.0 \times 10^9/\text{L}$  (Grade 2),  $< 50.0 \times 10^9/\text{L}$  to  $\geq 25.0 \times 10^9/\text{L}$  (Grade 3), and  $< 25.0 \times 10^9/\text{L}$  (Grade 4).

The above LLNs are defined as:

- Leukocytes:  $\text{LLN} = 4.0 \times 10^9/\text{L}$
- Neutrophils:  $\text{LLN} = 2.0 \times 10^9/\text{L}$
- Lymphocytes:  $\text{LLN} = 1.1 \times 10^9/\text{L}$
- Platelets:  $\text{LLN} = 150 \times 10^9/\text{L}$

### **6.13.5. Vital Signs and Other Physical Findings**

Vital signs and physical characteristics include systolic blood pressure (mmHg), diastolic blood pressure (mmHg), pulse (bpm), weight (kg), BMI ( $\text{kg}/\text{m}^2$ ), and body temperature ( $^{\circ}\text{C}$ ).

A by-patient listing of vital signs and physical characteristics (including scheduled visits, unscheduled visits, and repeat measurements) will be provided (Analysis population: FAS Population).

### **6.13.6. Electrocardiograms**

As a 12-lead electrocardiogram (ECG) will be locally performed only at screening visit (Visit 1), no ECG data analysis is planned in this study.

### **6.13.7. Columbia-Suicide Severity Rating Scale (C-SSRS)**

The C-SSRS is an assessment tool that evaluates suicidal ideation and behavior. Information on the C-SSRS scale can be found through the following link: <http://www.cssrs.columbia.edu>.

Specifically, the following outcomes are C-SSRS categories and have binary responses (yes/no). The categories have been re-ordered from the actual scale to facilitate the definitions of the composite and comparative endpoints, and to enable clarity in the presentation of the results.

Category 1 – Wish to be Dead

Category 2 – Non-specific Active Suicidal Thoughts

Category 3 – Active Suicidal Ideation with Any Methods (Not Plan) without Intent to Act

Category 4 – Active Suicidal Ideation with Some Intent to Act, without Specific Plan

Category 5 – Active Suicidal Ideation with Specific Plan and Intent

Category 6 – Preparatory Acts or Behavior

Category 7 – Aborted Attempt

Category 8 – Interrupted Attempt

Category 9 – Actual Attempt (non-fatal)  
Category 10 – Completed Suicide.

Self-injurious behavior without suicidal intent is also a C-SSRS outcome (although not suicide-related) and has a binary response (yes/no).

Composite endpoints based on the above categories are defined below.

- **Suicidal ideation:** A “yes” answer at any time during treatment to any one of the five suicidal ideation questions (Categories 1-5) on the C-SSRS.
- **Suicidal behavior:** A “yes” answer at any time during treatment to any one of the five suicidal behavior questions (Categories 6-10) on the C-SSRS.
- **Suicidal ideation or behavior:** A “yes” answer at any time during treatment to any one of the ten suicidal ideation and behavior questions (Categories 1-10) on the C-SSRS.

By-patient listings of C-SSRS and Self-Harm supplement and follow-up data will be provided (Analysis population: FAS Population). Given that few or no suicidal ideation or behaviors are anticipated, C-SSRS will be listed by patient and visit. Only patients that show suicidal ideation/behavior or self-injurious behavior without suicidal intent will be displayed (that is, if a patient’s answers are all ‘no’ for the C-SSRS, then that patient will not be displayed). However, if a patient reported any suicidal ideation/ behavior or self-injurious behavior without suicidal intent at any time point then all their ideation and behavior will be displayed, even if not positive. Note, missing data should not be imputed.

The *Self-Harm Supplement Form* in the eCRF is a one-question form that is completed, at any visit, including baseline visit, that asks for the number of suicidal behaviors, possible suicidal behaviors or nonsuicidal self-injurious behaviors the patient has experienced since the last assessment. For each unique event identified, a questionnaire (*Self-Harm Follow-Up Form* in the eCRF) which collects supplemental information on the self-injurious behavior is to be completed. The Self-Harm data will be listed by patient and visit if number of events on Self-Harm Supplement Form is not zero.

## 6.14. Immunogenicity

### 6.14.1. Definitions and Terms

The following sample- and patient-related definitions and parameters will be used to describe the immunogenicity data.

#### 6.14.1.1. Sample Category Definitions

[figure not shown]
Samples are classified into the following categories:

- **Unevaluable sample:** Sample could not be tested for anti-drug antibody (ADA) due to sample loss, mishandling, or errors in collection, processing, storage, etc.

- **Antidrug antibody (ADA) Positive sample:** The presences of ADA is detected and confirmed. The samples are reported as positive. If the sample is positive, a titer value is reported.
- **Neutralizing anti-drug antibody (NAb) Positive sample:** NAb are reported as detected.
- **ADA Negative sample:** The presence of ADA is not detected and the assay drug tolerance level is not exceeded.
- **NAb Negative sample:** The presence of NAb is not detected and the assay drug tolerance level is not exceeded.
- **Inconclusive sample:** when ADA/NAb is not detected in a sample but drug is present in the same sample at a level that can cause interference in the ADA/NAb detection method, then the negative ADA/NAb result cannot be confirmed and the sample should be considered inconclusive.
  - Using the psoriasis disease-specific cut point, the upper limit of drug tolerance in the ADA assay is 480.5 µg/mL and the upper limit of drug tolerance in the NAb assay is 1100 ng/mL. Confirmation of a negative ADA result is based on measured ixekizumab levels. Ixekizumab concentration below the determined drug tolerance of the ADA/NAb assays allow for confirmation of negative ADA/NAb results.

Figure RHCV.6.1 illustrates the relationship of some of the above terms.

Abbreviation: ADA = anti-drug antibody.

[figure not shown]
**Figure RHC.V.6.1. Sample definitions.**

#### 6.14.1.2. Patient Category Definitions

The following categories are applied to patients based on the classification of their samples:

- **Unevaluable patient:** a) a patient with no evaluable baseline sample and/or no evaluable post-baseline samples; b) a patient with an evaluable baseline sample but no evaluable post-baseline sample; c) a patient with no evaluable baseline sample, but whose evaluable post-baseline values are all ADA positive or a mix of positive and negative. (Note: If all post-baseline samples are negative, the patient is considered 'evaluable' and will be classified as ADA-negative.)
- **Evaluable patient:** a) Patient with an evaluable baseline sample and at least 1 evaluable post-baseline sample (that is, sample after administration of study drug); b) patient with no evaluable baseline sample whose evaluable post-baseline samples are all ADA negative.

Figure RHC.V.6.2 illustrates the relationship of the above terms.

[figure not shown]

**Figure RHCV.6.2. Patient categories (evaluable/unevaluable) based on sample status at baseline and post-baseline.**

**6.14.1.3. Definitions for Clinical Interpretation of Assay Results**

- **Baseline:** For immunogenicity summaries, baseline is the last nonmissing observation on, or prior to, the date of the first injection of study treatment of ixekizumab (Week 0).
- **Baseline ADA positive (preexisting antibody):** ADA detected in a sample collected at baseline.
- **TE-ADA positive:** a) a patient with a  $\geq 4$ -fold (or 2 dilutions) increase over a positive baseline antibody titer; or b) for a negative baseline titer, a patient with an increase from the baseline to a level of  $\geq 1:10$ .
- **Baseline ADA-negative:** ADA is not detected in a sample collected at baseline.
- **TE-ADA inconclusive patient:** A patient without a TE-ADA positive sample and with at least 1 sample for which drug levels may interfere with the ADA assay.
- **TE-ADA negative patient:** A patient who is evaluable for TE-ADA and is not either TE-ADA positive or TE-ADA inconclusive.

Figure RHCV.6.3 illustrates the relationship of some of these terms.

[figure not shown]
Abbreviation: ADA = anti-drug antibody.

**Figure RHCV.6.3. Relationship of terms for clinical interpretation of assay results for evaluable patients.**

All ADA positive samples will be evaluated for NAb. Definitions for NAb patient status will be defined as follows:

- **NAb-positive patient:** A patient where a NAb positive result is detected for  $\geq 1$  TE-ADA positive samples.
- **NAb-inconclusive patient:** A patient without a NAb positive sample and with at least 1 sample for which drug levels may interfere with the NAb assay.
- **NAb-negative patient:** A patient who is evaluable for NAb and is not either NAb positive sample or NAb inconclusive.

A flow chart that reflects the connection between the analytical test results and the clinical interpretation based on the definitions is shown in [Figure RHCV.6.4](#).

Abbreviation: ADA = anti-drug antibody.

**Figure RHCV.6.4. Flow chart of ADA assessment with clinical interpretation of the various result possibilities.**

### 6.14.2. Immunogenicity Analyses

Immunogenicity evaluable patients will be grouped into TE-ADA status groups as follows:

#### **TE-ADA Status Groups:**

- TE-ADA status (positive, negative, or inconclusive);
- NAb status (positive, negative, or inconclusive) for TE-ADA positive patients; and
- TE-ADA titer groups for TE-ADA positive patients:

- Low Titer: TE-ADA titer value (LOCF) <1:160;
- Moderate Titer: TE-ADA titer value (LOCF)  $\geq$ 1:160 and <1:1280; and
- High Titer: TE-ADA titer value (LOCF)  $\geq$ 1:1280.

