9.4.4. Immunogenicity Assessments

Samples for immunogenicity testing will be collected at time points indicated in the Schedule of Activities (Section 2). Venous blood samples will be collected into tubes and used to determine antibody production against ixekizumab. The actual date of each sampling will be recorded on the laboratory requisition.

Immunogenicity will be assessed by a validated assay designed to detect ADAs in the presence of ixekizumab. Antibodies may be further characterized and/or evaluated for their ability to neutralize the activity of ixekizumab. Treatment-emergent immunogenicity is defined as any occurrence of a 4-fold or 2 dilution increase in titer over the pretreatment baseline titer. In the case of a negative result at baseline, treatment-emergent immunogenicity is defined as an increase in titer to $\geq 1:10$. Immunogenicity samples will also be analyzed for ixekizumab serum concentration to facilitate the interpretation of the immunogenicity data at Week 12 (Visit 6), Week 20 (Visit 10) and ETV.

In the event of serious drug hypersensitivity reactions (such as generalized urticaria and/or anaphylaxis), additional samples will be collected as close to the onset of the event as possible and approximately 30 days following the event to evaluate antidrug antibodies (ADA), LY2439821 serum concentration, and additional exploratory biomarkers of hypersensitivity which could include tryptase, complement levels and cytokine measurements.

Samples will be retained for a maximum of 15 years after the last patient visit, or for a shorter period if local regulations and ERBs allow, at a facility selected by the sponsor. The duration allows the sponsor to respond to future regulatory requests related to ixekizumab. Any samples remaining after 15 years will be destroyed.

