10.3.6. Evaluation of Immunogenicity

The frequency of patients with preexisting ADA and with TE ADA+ to ixekizumab will be tabulated. Treatment-emergent ADAs are defined as those with a titer 2-fold (1 dilution) greater than the minimum required dilution if no ADAs were detected at baseline (treatment-induced ADA) or those with a 4-fold (2 dilutions) increase in titer compared to baseline if ADAs were detected at baseline (treatment-boosted ADA). For the TE ADA+ patients the distribution of maximum titers will be described. The frequency of neutralizing antibodies will also be tabulated in TE ADA+ patients.

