### **6.3.2. Last Observation Carried Forward (LOCF)**

Continuous efficacy and health outcomes variables will be summarized using a last observation carried forward (LOCF) method. For patients discontinuing study treatment for any reason, the last non-missing post-baseline observation before the missing data will be carried forward to the corresponding time point for evaluation. Enrolled patients without at least 1 post-baseline observation will not be included for evaluation.

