#### **6.14.2.1. Analyses of Characteristics of ADA Immune Response**

Overall ADA effects will be summarized on all evaluable patients within the following study periods and analysis populations:

- Period 2 (Analysis population: FAS Population)
- Combined Periods 2 and 3 (Analysis population: Maintenance Dosing Period Population).

The overall frequency of patients will be summarized for the TE-ADA status groups. Scheduled visits, unscheduled visits, and repeat measurements will be included.

A by-patient listing to include visit, sample date, injection date, ADA result, ADA titer value, TE-ADA result, NAb result, ixekizumab concentration, and GIS result will be provided (Analysis population: FAS Population).

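### SAP 6.14.2 groups TE-ADA-positive patients by LOCF titer and plans no preexisting-ADA count, where Protocol 10.3.6 specifies maximum titers and that count

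*SAP*

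**What the plan says.** Protocol 10.3.6 plans three immunogenicity summaries. The first is a count: "The frequency of patients with preexisting ADA and with TE ADA+ to ixekizumab will be tabulated". The second concerns titers: "For the TE ADA+ patients the distribution of maximum titers will be described". The third is the frequency of neutralizing antibodies (NAb) among TE-ADA-positive patients.

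SAP 6.14.2 keeps the NAb summary but sorts TE-ADA-positive patients into three titer groups by a carried-forward value. The lowest is "Low Titer: TE-ADA titer value (LOCF) <1:160"; Moderate runs from 1:160 to below 1:1280, and High starts at 1:1280. SAP 6.14.2.1 then states what is tabulated: "The overall frequency of patients will be summarized for the TE-ADA status groups". Those groups are TE-ADA status, NAb status and titer group. The tabulation is made for Period 2 on the FAS and for Combined Periods 2 and 3 on the Maintenance Dosing Period Population, and it includes unscheduled and repeat samples.

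SAP 6.14.1.3 does define preexisting antibody ("ADA detected in a sample collected at baseline"), but no planned summary counts it. The general imputation rule in SAP 6.3.2 reads: "Continuous efficacy and health outcomes variables will be summarized using a last observation carried forward (LOCF) method". It does not mention titers.

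**The concern.** TE-ADA positivity is an any-time status: under SAP 6.14.1.3 a single qualifying sample is enough. The titer group, by contrast, comes from the carried-forward value. A patient can therefore be TE-ADA positive because of the Week 12 sample and be graded on a lower titer at Week 20 or the early termination visit (ETV). The protocol's maximum would show the peak response; the SAP's table might not.

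The missing baseline count is a separate matter. Baseline status decides which TE-ADA criterion applies to a patient (a 4-fold rise over a positive baseline, or reaching 1:10 from a negative one), so the count gives context for the TE-ADA result. At stake is whether the immunogenicity table delivers what the protocol promised and shows the strongest antibody response of each TE-ADA-positive patient.

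**Working it through.** No sample size, power or error rate is involved, and the plan states no figure to reproduce. The check compares the texts and then applies the SAP's cut-offs to possible titers.

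**1. Side by side**

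| Item | Protocol 10.3.6 | SAP 6.14.2 and 6.14.2.1 |
|---|---|---|
| Titer in TE-ADA-positive patients | Maximum, distribution described | LOCF value, three groups |
| Preexisting ADA | Tabulated | Defined in 6.14.1.3, not tabulated |
| NAb in TE-ADA-positive patients | Tabulated | Tabulated |

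**2. How many titers a patient can have.** The Schedule of Activities places immunogenicity samples at Week 0, Week 12, Week 20 and ETV. A patient normally has one scheduled post-baseline sample in Period 2, and two in Combined Periods 2 and 3 (Week 12, then Week 20 or ETV). With one post-baseline titer, last and maximum are the same.

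**3. Direction.** For any set of post-baseline titers, last ≤ maximum. The groups are ordered by titer, so group(last) ≤ group(maximum). A difference can only be downward.

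**4. Examples, Week 12 then Week 20/ETV (hypothetical titers)**

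| Titers | LOCF group | Maximum group |
|---|---|---|
| 1:160, then 1:80 (160/80 = 2, one dilution) | Low | Moderate |
| 1:320, then 1:20 | Low | Moderate |
| 1:1280, then 1:80 (1280/80 = 16, four dilutions) | Low | High |
| 1:640, then 1:160 | Moderate | Moderate |
| 1:20, then 1:1280 | High | High |

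**5. All ordered pairs.** Assume a 2-fold titer grid starting at 1:10 (the documents equate 4-fold with 2 dilutions) and a titer reported at both visits. The grid has 4 Low values (1:10 to 1:80), 3 Moderate values (1:160 to 1:640), and h High values, depending on an assumed upper end. The last titer falls in a lower group in 3×4 + h×4 + h×3 = 12 + 7h pairs.

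- Upper end 1:1280, h = 1: 19 of 8×8 = 64
- Upper end 1:2560, h = 2: 26 of 9×9 = 81
- Upper end 1:5120, h = 3: 33 of 10×10 = 100

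The last titer falls in a higher group in none. These are counts of possible pairs, not probabilities; the documents give no information on how often titers fall.

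**6. LOCF for titers.** SAP 6.14.1.1 reports a titer only for a positive sample. If Week 12 is positive and Week 20 negative, the plain reading carries the Week 12 titer forward, and the two rules agree. The SAP does not say this. Nor does it say whether a later positive sample that no longer meets the TE-ADA criterion counts. For example, take a baseline of 1:20, Week 12 at 1:160 (160/20 = 8-fold, qualifies) and Week 20 at 1:40 (40/20 = 2-fold, does not). Carrying forward the last qualifying titer gives Moderate; taking the last reported titer gives Low. A maximum needs no such rule.

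**The case against.** The strongest reply is that little depends on this, and most of that reply stands.

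- A reader might infer that the secondary endpoint is understated. It is not. The endpoint is the number of patients who develop TE-ADA and NAb, and neither status uses the last titer. The Low, Moderate and High grouping is not a listed endpoint.
- A reader might infer that leaving out the preexisting-ADA count also understates the response. It does not; it omits a specified tabulation.
- One misgraded patient might be presented as 20% of a disease group of 5. That is the wrong denominator: titer groups cover only TE-ADA-positive patients, whose number is unknown, and categorical data are reported as frequency counts.
- The by-patient listing in SAP 6.14.2.1 gives ADA result and titer by visit. With 12 planned patients, each maximum can be read off, and baseline ADA too if the listing includes the baseline visit.
- The SAP's silence about the change carries little weight. SAP 6.1 declares a different departure, but Protocol 10.3.1 requires non-principal analysis changes to be described and justified in the study report, not in the SAP. The SAP revision history covers changes from Version 1 to Version 2 only.
- A reader might also see conflicting TE-ADA thresholds for a negative baseline. Protocol 9.4.4 says "In the case of a negative result at baseline, treatment-emergent immunogenicity is defined as an increase in titer to" at least 1:10, while 10.3.6 uses 2-fold above the minimum required dilution. These agree if that dilution is 1:5 (2×5 = 10). The documents do not state it, and a conflict appears only if another value, such as 1:10, is assumed. SAP 6.14.1.3 uses at least 1:10, as 9.4.4 does, so the analysis rule is settled.

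None of this removes the mismatch: two summaries specified in the protocol are missing from the SAP's plan, and the titer rule that replaces one of them is undefined.

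**Conclusion.** The point holds as a minor protocol/SAP mismatch in two descriptive immunogenicity summaries. In Combined Periods 2 and 3, or wherever unscheduled or repeat samples exist, a TE-ADA-positive patient whose titer falls across 1:160 or 1:1280 is graded lower than the protocol's maximum would give, and never higher. A single 2-fold fall is enough at a boundary. How many patients this would affect cannot be estimated from the documents.

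The conclusion assumes that LOCF means the last reported post-baseline titer. If it means the last qualifying titer, some of the differences disappear, which is itself a reason to define it. The omission of the preexisting-ADA count does not depend on that assumption. Because the titers stay in the listing, the gap is in the planned tables and not in the data.

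**What to change.** In SAP 6.14.2, classify TE-ADA-positive patients by maximum post-baseline titer within the analysis period. Alternatively, keep the LOCF groups, show the maximum-titer groups beside them, and define LOCF for titers, including what happens when a later sample is negative or no longer meets the TE-ADA criterion. In SAP 6.14.2.1, add the number of patients with preexisting (baseline-positive) ADA. Replacing LOCF outright is not necessary if the maximum-titer summary is added.

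The cost is a few words and one or two extra table rows. No new samples are needed.
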